6.4 Safety Follow-up

A 30-day safety follow-up telephone contact is to be completed for subjects who complete the treatment period of the study as well as those who discontinue prematurely from the study. Subjects should have the following completed at least 30 days after last dose of study drug:

- Assessment of concomitant medications/treatments
- Assessment of AEs

6.5 Unscheduled Visits

Unscheduled visits may occur as determined by the Investigator and may include any safety evaluations deemed by the Investigator to be clinically indicated. The following safety assessments will typically be performed; however, these are not required and other assessments besides the following may be performed as needed: assessment of AEs, assessment of concomitant medications/treatments, measurement of vital signs, and suicidality assessment.

7 ADVERSE EVENTS

7.1 Specification of Safety Parameters

7.1.1 Definition of Adverse Event

An AE is defined as “any untoward medical occurrence in a patient or clinical study participant, temporally associated with the use of study drug, whether or not considered related to study drug”.

An AE can therefore be any unfavorable and unintended sign (e.g., an abnormal laboratory finding), symptom, or disease temporally associated with the use of a drug, without any

judgment about causality or seriousness. An AE can arise from any use of the drug (e.g., off-label use, use in combination with another drug) and from any route of administration, formulation, or dose, including an overdose.

A suspected adverse reaction is any AE for which there is a reasonable possibility that the drug caused the AE.

AEs do not include the following:

- Stable or intermittent chronic conditions (such as myopia requiring eyeglasses) that are present prior to Baseline and do not worsen during the study
- Medical or surgical procedures (e.g., surgery, endoscopy, tooth extraction, transfusion). The condition that leads to the procedure is an AE if not present at Baseline.
- Overdose of concomitant medication without any signs or symptoms unless the subject is hospitalized for observation
- Hospitalization for elective surgery planned prior to study (situation where an untoward medical occurrence has not occurred)
- Pregnancy will not be considered an AE, but if it occurs, it will be reported on a pregnancy form

7.1.2 Definition of Serious Adverse Event

In addition to the severity rating, each AE will be classified by the Investigator as “serious” or “not serious.” The seriousness of an event will be defined according to the applicable regulations and generally refers to the outcome of an event. An SAE is one that meets one or more of the following:

- Is fatal
- Is immediately life threatening
- Results in disability or permanent damage
- Requires hospitalization
- Prolongs existing hospitalization
- Is a congenital anomaly or birth defect (in an offspring)
- Is medically significant

Definition of Life Threatening

A life threatening event places the subject at immediate risk of death from the event as it occurred. This does not include an AE, which, had it occurred in a more severe form, might have caused death.

Definition of Hospitalization

Hospitalization is defined by the Sponsor as a full admission to the hospital for diagnosis and treatment. This includes prolongation of an existing inpatient hospitalization.

Examples of visits to a hospital facility that do not meet the serious criteria for hospitalization include:

- Emergency room visits (that do not result in a full hospital admission)
- Outpatient surgery
- Preplanned or elective procedures
- Protocol procedures
- Social hospitalization, defined as admission to the hospital as a result of inadequate family support or care at the subject's primary residence

Definition of Disability or Permanent Damage

Disability is defined as a persistent or significant incapacity or substantial disruption of the ability to conduct normal life functions.

Definition of Medically Significant

Important medical events (medically significant events) that may not result in death, be life threatening, or require hospitalization may be considered to be an SAE when, based upon appropriate medical judgment, they may jeopardize the subject or may require medical or surgical intervention to prevent one of the outcomes listed in this definition. Examples of such events are intensive treatment in an emergency room or at home for allergic bronchospasm, blood dyscrasias, or convulsions that do not result in hospitalization or development of drug dependency or drug abuse.

An SAE may also include any other event that the Investigator or Medical Monitor judges to be serious or that suggests a significant hazard, contraindication, side effect, or precaution.

7.2 Classification of an Adverse Event

7.2.1 Severity of Event

The severity of each AE will be graded on a 3-point scale and reported in detail as indicated on the eCRF:

- **Mild:** awareness of sign or symptom but easily tolerated, causing minimal discomfort, and not interfering with normal everyday activities
- **Moderate:** sufficiently discomforting to interfere with normal everyday activities
- **Severe:** incapacitating and/or preventing normal everyday activities

7.2.2 Relationship to Study Drug

The causality of each AE should be assessed and classified by the Investigator as “related” or “not related.” An event is considered related if there is a reasonable possibility that the event may have been caused by the product under investigation (i.e., there are facts, evidence, or arguments to suggest possible causation).

Consider the following when assessing causality:

- Temporal associations between the agent and the event
- Response to cessation (de-challenge) or re-challenge
- Compatibility with known class effect
- Known effects of concomitant medications
- Pre-existing risk factors
- A plausible mechanism
- Concurrent illnesses

7.2.2.1 Duration

The start and stop dates for AEs will be recorded using the following criteria:

- **Start:** Date of the first episode of the AE or date of significant sustained worsening in severity
- **Stop:** Date when AE either ceased permanently or changed in severity

7.2.2.2 Frequency

The frequency of the AE should be indicated according to the following definitions:

- **Single:** Experienced once, without recurrence

- **Recurrent:** More than one discrete episode with the same severity

7.2.2.3 Action Taken With Study Drug

- **Dose not changed:** No change in study drug
- **Drug interrupted:** Study drug temporarily stopped
- **Drug withdrawn:** Study drug discontinued permanently
- **Not applicable**
- **Unknown**

7.2.2.4 Therapy

- **None:** No new treatment instituted
- **Medication:** New treatment initiated as a direct result of AE
- **Other:** Other action required

7.2.2.5 Outcome

- **Recovered/resolved:** Recovered or resolved
- **Recovered/resolved with sequelae:** Recovered or resolved with sequelae
- **Not recovered/not resolved:** Not recovered or not resolved
- **Fatal:** Death due to an AE
- **Unknown:** Unknown

7.2.2.6 Seriousness

- **Not serious**
- **Serious**

7.2.3 Definition of Unexpectedness

An AE, the nature or severity of which is not consistent with the information provided in the Reference Safety Information section of the current pimavanserin Investigator's brochure.

7.3 Time Period and Frequency for Event Assessment and Follow-up

Adverse events will be recorded from the time informed consent is obtained through the safety follow-up period. All AEs must be either resolved or stable at the end of the safety follow-up period. If ongoing at the end of the safety follow-up period, the subject should be referred for appropriate treatment.

In the event that a subject discontinues and has an ongoing AE at the time of discontinuation ([Section 4.4.1](#)) or is withdrawn from the study because of an AE, the subject should be followed and treated by the Investigator until the AE has resolved, stabilized, or a new chronic baseline has been established.

7.4 Reporting Procedures

7.4.1 Adverse Event Reporting

The Investigator must record all observed AEs and all reported AEs. At each visit, the Investigator should ask the subject a nonspecific question (e.g., “Have you noticed anything different since your last visit?”) to assess whether any AEs have been experienced since the last report or visit.

Note that any use of medication (and specifically any newly prescribed medication) during the course of a study may indicate the occurrence of an AE that may need to be recorded on both the AE and the concomitant medication page.

All AEs, serious and not serious, will be recorded on the AE eCRF page using appropriate medical terminology. Severity and relationship to study drug will be assessed by the Investigator.

When possible, clinical AEs should be described by diagnosis and not by symptoms (e.g., “cold” or “seasonal allergies” instead of “runny nose”).

All AEs, *whether or not related to the study drug*, must be fully and completely documented on the AE eCRF and in the subject’s notes.

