1.3.1 Parkinson's Disease Psychosis Program

The scope of the development program for pimavanserin is the largest ever conducted in PDP. At the time of approval, 616 mostly older, late-stage PDP subjects had been evaluated in 16 countries over a span of >10 years. Clinically meaningful efficacy was established in Study ACP-103-020, a 6-week, placebo-controlled Phase 3 study ([Cummings et al. 2014](#)). This efficacy was supported by data from additional short-term Phase 2b/3 studies. In ACP-103-020, pimavanserin 34 mg consistently demonstrated statistically significant efficacy across multiple and independent endpoints, subject subgroups, and sensitivity analyses. Improvements in sleep and daytime wakefulness were also observed. These clinical benefits were achieved without worsening of PD motor symptoms and without a number of other safety concerns associated with atypical antipsychotics.

Pimavanserin is considered to be generally safe and well tolerated in patients with PDP. Across all clinical studies of pimavanserin, the most frequently reported treatment-emergent adverse events (TEAEs) were in the central nervous system (CNS), gastrointestinal, and psychiatric systems. Most events were mild to moderate in intensity. The most common CNS TEAEs included dizziness (including postural), headache, and somnolence (drowsiness). Common gastrointestinal disturbances included dyspepsia, nausea, constipation, and vomiting. Severe nausea and vomiting were dose limiting in a few cases. Reported psychiatric conditions included agitation, insomnia, and confusional state.

Clinical and nonclinical safety pharmacology studies of pimavanserin suggest a potential risk for QT interval (QT) prolongation. The magnitude of effect in humans has been assessed in a thorough QT study with doses of pimavanserin ranging from 17 to 68 mg. In the Phase 3 PDP program, an average prolongation of approximately 5 to 8 ms was observed with pimavanserin 34 mg.

Additional information is provided in the pimavanserin IB and in the NUPLAZID® (pimavanserin) US package insert.

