1.4 Study Rationale

Onset and progression of disability are major factors in the diagnosis and management of PD (Shulman 2010; Shulman et al. 2008). The World Health Organization (WHO) defines disability as “any restriction or lack of ability to perform an activity within the range considered normal for a human being due to an impairment” (World Health Organization 1980). In this context, “disability” is an umbrella term for the negative aspects of the interaction between an individual with a health condition and environmental and personal factors, in contrast to “functioning,” an umbrella term for the positive aspects of this interaction (World Health Organization 2001). Accurate assessment of disability is important given that the onset of functional limitations triggers changes in clinical management, including adjustment of medications or referral for deep brain stimulation (DBS) surgery. Neurological examination of PD-related impairments, including tremor, bradykinesia, gait, and cognitive function, does not provide adequate insight into the capacity for performance of daily activities because there is a broad range of compensatory strategies and support based on socioeconomic status. Patient insight into daily function also varies with PD patients tending to underestimate their level of disability (Shulman et al. 2006). Therefore, integrating data from multiple sources (examination, disability assessment, and patient and caregiver reports) is important.

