4.1 Inclusion Criteria

A subject must meet all of the following inclusion criteria to be eligible for participation in the study:

1. Male or female subjects at least 40 years of age
2. Can understand the nature of the study and protocol requirements and provide written informed consent
3. Is able to demonstrate the ability to complete subject-reported outcome measures on a handheld device, and can be reliably rated on assessment scales (in the opinion of the Investigator)
4. Must be able to designate a caregiver or study partner who the subject agrees can provide reliable information on the subject's well-being, and is willing to provide written informed consent, and to attend clinic visits with the subject

5. Has a Schwab & England ADL Scale score of 40-80% (inclusive) at both Visit 1 (Screening) and Visit 2 (Baseline) as it relates to their PDP symptoms
6. Has a Mini-Mental State Examination (MMSE) score ≥ 19 at Screening
7. *This criterion has been deleted; please consult the Summary of Changes for details.*
8. Has a diagnosis of idiopathic Parkinson's disease (PD), according to the Movement Disorders Society criteria for the diagnosis of PD ([Postuma et al. 2015](#)), without any other known or suspected cause of parkinsonism. History of initial PD symptoms onset greater than 1 year prior to Screening
9. Has psychotic symptoms that may impair function and are severe enough to warrant treatment with an antipsychotic agent
10. Has a CGI-S score of ≥ 4 when assessing psychosis symptoms at Visit 1 (Screening) and Visit 2 (Baseline)
11. If the subject is on anti-Parkinsonian medication, they must be on a stable regimen for 2 months prior to Baseline and not planning (at the time of the Baseline visit) to make a change in dose(s)
12. *This criterion has been deleted; please consult the Summary of Changes for details.*
13. *Psychotic symptoms developed after the onset of symptoms of PD*
14. Psychotic symptoms present for at least 1 month overall (could be intermittent), with active psychotic symptoms in either of the last 2 weeks prior to screening
15. Has clear sensorium at study entry (i.e., oriented to time, person, and place) in the opinion of the Investigator
16. If the subject is female, she must not be pregnant or breastfeeding. She must also be of non-childbearing potential (defined as either surgically sterilized or at least 1 year postmenopausal) OR must agree to use TWO clinically acceptable methods of contraception

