7.4.2 Serious Adverse Event Reporting

The reporting of SAEs by the Sponsor or designee to the regulatory authorities is a regulatory requirement. Each regulatory authority has established a timetable for reporting SAEs based upon established criteria.

Serious AEs must be reported within 24 hours of discovery to the Sponsor or its designee; use the appropriate form for initial and/or follow-up reporting.

At a minimum, events identified by the Sponsor to require expedited reporting as serious, unexpected, and related to study drug must be brought to the attention of the responsible Institutional Review Board (IRB), as per applicable regulations. These will be provided by the Sponsor after their assessment. It is the Investigator’s responsibility to provide these expedited reports, and any new and significant information, to the responsible IRB.

When an SAE occurs, Investigators will review all documentation related to the event and will complete the paper SAE form (for initial and/or follow-up information) and fax or email (within 24 hours of discovery) to the contact information provided on the SAE form.

Subjects will be followed through the safety follow-up period for 30 days after last dose of study drug for any SAEs and/or other reportable information until such events have resolved or the Investigator, in conjunction with the Sponsor, deems them to be chronic or stable.

In the event of any SAE (other than death), the study subject will be instructed to contact the Investigator (or designee) using the telephone number provided in the informed consent form (ICF). All subjects experiencing an SAE will be seen by the Investigator or designee as soon as is feasible following the report of the SAE.

Serious AEs occurring greater than 30 days after last dose of study drug should be reported if in the judgment of the Investigator there is “a reasonable possibility” that the event may have been caused by the product.

SAEs should also be reported to the institutional review board/ethics committee (IRB/EC) according to local regulations.

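### Adverse events are actively asked about only of the subject; the caregiver whom the protocol requires as a reliable informant is never asked, so TEAEs may be under-ascertained

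*Protocol*

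**What the plan says.** Protocol Section 7.4.1 sets the method of elicitation: "At each visit, the Investigator should ask the subject a nonspecific question". Just before that it sets the recording rule, which does not depend on who reports: "The Investigator must record all observed AEs and all reported AEs". It adds a second trigger, noting that "any use of medication (and specifically any newly prescribed medication) during the course of a study may indicate the occurrence of an AE".

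For serious events other than death, Section 7.4.2 says that "the study subject will be instructed to contact the Investigator (or designee) using the telephone number provided in the informed consent form". The caregiver is not mentioned. Section 6.4 lists adverse event assessment among the tasks of the safety follow-up call without saying who is to be asked. SAP Section 13.1 defines and tabulates TEAEs and says nothing about the informant.

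Inclusion criterion 4 reads in part: "Must be able to designate a caregiver or study partner who the subject agrees can provide reliable information". That person must also be willing to consent in writing and come to clinic visits, and Section 12.3.2 requires the consent before any screening procedure. Under Section 6, visits may take place at home, and the caregiver must then be present.

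**The concern.** The protocol chose active elicitation and named one informant, although a second, suitable one is normally at hand. Entry requires a CGI-S of at least 4 for psychosis and permits an MMSE as low as 19. Somnolence is listed in Section 1.3.1 among the most common nervous system events, and of psychiatric events the section says: "Reported psychiatric conditions included agitation, insomnia, and confusional state". A companion may notice such events more readily than the person affected. From Week 4 onward the scheduled visits are four weeks apart, so the question relies on recall over that interval. After Week 16 the only scheduled contact is a telephone call, although events still count as TEAEs up to 30 days after the last dose.

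TEAEs are the first-named safety endpoint. With a single arm, incidence is reported as observed, so any under-ascertainment goes directly into the reported rates. The contact instruction raises a separate question of timeliness: a subject who is confused or has been admitted to hospital may not be able to make the call.

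**Working it through.** **Step 1. Who is named, and for what.**

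| Task | Source | Informant named |
|---|---|---|
| Adverse event question at each visit | Protocol 7.4.1 | Subject |
| Contact with the site about a serious event | Protocol 7.4.2 | Subject |
| Adverse event assessment at the follow-up call | Protocol 6.4 | None |
| TEAE definition and tables | Protocol 9.5.4.1, SAP 13.1 | None |
| Schwab and England scale | SAP 5.2.5 | Subject and caregiver, independently |
| MDS-UPDRS Part IA | Protocol 6.2.3 | Investigator, using patient and caregiver information |
| NPI-Q nighttime behavior | Protocol 6.2.9, SAP 5.2.3 | Informant, typically the caregiver |
| Compliance when drug cannot be returned | Protocol 5.1.6 | Subject or caregiver |

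The caregiver is an explicit source for function, symptoms and even lost capsules. For adverse events, no section tells the investigator to ask the caregiver.

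**Step 2. The plan's own numbers.** Protocol Section 3.1 gives 89 screened, 53 enrolled and 42 completers, with 40% screen failure and 20% dropout.

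- 89 × (1 − 0.40) = 53.4, stated as 53.
- 53 × (1 − 0.20) = 42.4, stated as 42.

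Both reproduce. The illustration below uses 53 as the number treated.

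**Step 3. Illustration of what incomplete detection does.** The documents give neither a true incidence nor a detection fraction, so both are assumed. Let p be the true proportion of subjects with a given event and d the fraction of those cases that are detected, with subjects independent.

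P(no reported case) = (1 − p × d)^53

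For p = 5%:

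- d = 100%: 0.95^53 = 0.066
- d = 80%: (1 − 0.04)^53 = 0.96^53 = 0.115
- d = 60%: (1 − 0.03)^53 = 0.97^53 = 0.199

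For a commoner event, p = 15%, the expected number of reported cases is 53 × 0.15 × d:

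- d = 100%: 8.0
- d = 80%: 6.4
- d = 60%: 4.8

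**Step 4. How far the illustration reaches.** It shows the sensitivity of a 53-subject study to incomplete detection. It does not measure the gain from asking the caregiver. That gain is the difference between the present system and the present system plus one more question, and it cannot be derived from the documents. The 100% row is a reference that neither system would reach.

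**The case against.** The strongest case on the other side is that much caregiver information already reaches the investigator. MDS-UPDRS Parts I and II, in patient and caregiver versions, are scheduled at every clinic visit. The Part I items in SAP Section 5.2.6.1 include cognitive impairment, sleep problems, daytime sleepiness, constipation and light-headedness on standing, which overlap several of the drug's listed events. The informant also completes the NPI-Q nighttime item from Baseline on. An investigator who sees these ratings must record any adverse event observed. This stands and narrows the gap. It does not close it: no rule turns such a rating into an adverse event, and agitation is not directly covered.

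Stronger readings are tempting, and the documents do not support them:

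- *Adverse events come from the subject alone.* They do not. Section 7.4.1 requires all observed and reported events to be recorded, whatever the source, and new medication is a further prompt.
- *The subject is the least reliable source, being psychotic throughout.* This is not shown. Subjects must give their own consent, be reliably ratable and have a clear sensorium at entry. An MMSE of 19 is a floor. The psychosis criteria describe entry, and symptoms may be intermittent.
- *Section 1.4 already requires caregiver reports here.* It says "Patient insight into daily function also varies with PD patients tending to underestimate their level of disability" and calls integrating several sources important. Its subject is daily function and disability, not recall of adverse events.
- *The safety objective rests on this question.* The endpoints also include the C-SSRS and potentially clinically important findings on examination, laboratory tests, vital signs and ECG.

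Two further limits apply. The caregiver's consent form is not among the documents, so whether it asks caregivers to report events or telephone the site cannot be judged. And a question asked at visits does nothing for delay between visits; only a change to the contact instruction bears on that.

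**Conclusion.** The point holds as an omission in elicitation. The only scripted adverse event question and the only serious-event contact instruction name the subject, while a consenting caregiver, required to be a reliable informant, is not asked. TEAEs that an onlooker would notice first may therefore be under-ascertained, and there is no control arm that would share the shortfall.

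The size is unknown. The figures of 6.6%, 11.5% and 19.9% rest on an assumed 5% incidence, assumed detection fractions, 53 treated subjects and independence between subjects; they are not estimates for this trial. Nothing here invalidates the safety analysis of a descriptive, single-arm Phase 4 study in an approved indication. The case for acting is that the improvement is inexpensive and the informant is already in place.

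**What to change.** - **Protocol 7.4.1:** have the investigator put the nonspecific question at each visit to the subject and also to the caregiver or study partner.
- **Protocol 6.4:** state that at the safety follow-up call the same question goes to both.
- **Protocol 7.4.2:** instruct both the subject and the caregiver or study partner to contact the site about a serious event.
- **Optional:** add a field for the source of the report to the adverse event eCRF page.

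The cost is a few sentences of protocol text, about one minute per visit and, if adopted, one eCRF field. No dose, eligibility criterion or analysis rule changes. The downside is that counts may rise slightly and become less comparable with studies that asked subjects only. Recording the source would let a reader see how many events came from the caregiver.
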